9 STUDY PROCEDURES

9.1 Screening

For screening procedures see the Schedule of Events and the Assessments Section. Screening activities may only begin after a subject has signed consent. All screening activities must take place within 21 days prior to cycle one day one unless otherwise noted.

9.2 Treatment Period

Once a subject has completed screening, has been found to be eligible, and has been registered, treatment procedures may begin. The start of a new cycle of therapy may be delayed up to 7 days to allow for holidays or patient preference. See the Schedule of Events and the Assessments Section for treatment period procedures.

9.3 End of Treatment

Upon discontinuation of study treatment, an End of Treatment visit will occur. The end of treatment visit should occur when the decision to discontinue treatment is made. If this visit overlaps with a regularly scheduled visit, only the procedures listed in the calendar for the EOT visit will be performed. For End of Treatment procedures see the Schedule of Events and the Assessments Section.

9.4 Long Term Follow-Up

Upon disease progression or initiation of a new anticancer therapy, patients will be followed for survival in long-term follow-up for a total of 36 months from the start of therapy. Patients will be contacted every three months (± 14 days) until the end of the study, patient withdrawal of consent, or death of any cause. Survival status may be collected by public records, medical records, or by contacting the patient by phone. All efforts should be made to contact the patient for these time points. Subjects who ended treatment per Amendment 6 (v.09DEC2025) should be followed for SOC dosing of cobimetinib. Community sourced cobimetinib will not be considered a new line of therapy if given at the same dose and frequency as outlined in the protocol.

9.4.1 Lost to follow-up

Patients will be considered lost to follow-up only if no contact has been established by the time the study is completed, such that there is insufficient information to determine the patient's status at that time. Patients who refuse to continue participation in the study, including telephone contact, should be documented as "withdrawal of consent" rather than "lost to follow-up." Investigators should document attempts to re-establish contact with missing patients throughout the study period. If contact with a missing patient is re-established, the patient should not be considered lost to follow-up and evaluations should resume according to the protocol.

To support key endpoints of OS analysis, the survival status of all patients in the full analysis and the safety analysis sets should be re-checked, this includes those patients who withdrew consent or are classified as "lost to follow up."

- Lost to Follow up – site personnel should check hospital records, the patients' current physician, and a publicly available death registry (if available) to obtain a current survival status.
- If the patient has actively withdrawn consent to the processing of their personal data, the survival status of the patient can be obtained by site personnel from publicly available death registries (if available) where it is possible to do so under applicable local laws to obtain a current survival status.

10 STUDY ASSESSMENTS

Every effort should be made to ensure that the protocol-required tests and procedures are completed as described. However, it is anticipated that from time to time there may be circumstances, outside of the control of the Investigator that may make it unfeasible to perform the test. In these cases, the Investigator will take all steps necessary to ensure the safety and well-being of the patient. When a protocol-required test cannot be performed, the Investigator will document the reason for this and any corrective and preventive actions that he or she has taken to ensure that normal processes are adhered to as soon as possible.

10.1 Demographics and Medical History

Demographics and medical history will be collected at the time of screening for each eligible patient. The following information will be collected: age, gender, co-morbidities, prior cancers, prior cancer therapy, transfusion-dependence, smoking status, previous hypomethylating agent (HMA) therapy, and best response achieved on prior HMA therapy.

10.2 Physical Examinations and Vital Signs

Patients will have physical examinations to include major body systems, vital signs, assessment of ECOG performance status (see Appendix 1), weight and height (height will be measured at screening only) at the time points described in the Schedule of Events. If necessary to facilitate scheduling, physical exams may occur one day prior to study treatment.

Vital signs, including blood pressure, pulse rate, and temperature will be also recorded at the time points described in the Schedule of Events. Vital signs should be taken prior to the administration of any investigational product at the visit.

10.3 Adverse Events

Adverse events experienced during trial participation will be collected per the Schedule of Events and Adverse Events Section. Each study participant will be questioned about the occurrence of adverse events in a non-leading manner. Should the treating investigator feel that the adverse event is attributed to study therapy, then dose modification guidelines in Section 7.2 will be followed.

10.4 Mutation Testing

It is required that all patients have confirmation and documentation of the necessary RAS pathway activating mutation through local laboratory next-generation sequencing. The

mutational status must be confirmed by a local Clinical Laboratory Improvement Amendments (CLIA) certified laboratory.

Consistent with standard-of-care for patients with CMML, the institutional hematology sequencing will be used for the detection of single nucleotide variants and small insertions/deletions of diagnostic, prognostic, or other clinical significance in myeloid malignancies:

- University of Utah: ARUP Laboratories Myeloid Malignancies Mutation Panel by Next Generation Sequencing
<https://ltd.aruplab.com/Tests/Pub/2011117>
- Oregon Health & Science University: Knight Diagnostic Laboratories GeneTrails Hematologic Malignancies 220 Gene Panel
<https://knightdxlabs.ohsu.edu/home/test-details?id=GeneTrails+Hematologic+Malignancies+220+Gene+Panel>
- University of Washington/Fred Hutchinson Cancer Research Center: Myeloid Gene Panel by NGS (HCAPA)
<https://testguide.labmed.uw.edu/public/view/HCAPMY>

Genomic variants will be interpreted per 2017 guideline recommendations by AMP/ASCO/CAP using COSMIC, peer-reviewed literature, and AMP/CAP/ASCO variant classification guidelines. Variants detected on institutional sequencing panels will be considered “RAS pathway activating” if they are reported to be of known significance in myeloid malignancies on institutional sequencing panels and the variant interpretation (as reported by laboratory clinical variant scientists) is known or predicted to result in gain-of-function for positive regulators of RAS/MAPK signaling (i.e. *NRAS*, *KRAS*, *PTPN11*, *JAK2*, *BRAF*) or loss-of-function in negative regulators (i.e. *CBL*, *NF1*) of RAS/MAPK signaling.

10.5 12-Lead Electrocardiograms

All patients require a single 12-lead ECG measurement according to the Schedule of Events. The parameters to be recorded are QT, QTcF, PR, and QRS. A standard 12-lead (with a 10-second rhythm strip) tracing will be used for all ECGs. If the QTcF is prolonged (>500 msec) then a **triplicate** ECG should be conducted with two minutes between readings. Mean QTc will be calculated using the Fridericia calculation. If the mean QTcF is >500 msec (\geq Grade 3 QTcF prolongation), follow dose modification guidelines in Section 7.2.

10.6 Echocardiogram/MUGA

LVEF will be assessed by transthoracic echocardiogram or MUGA performed at the time points indicated on the Schedule of Events. LVEF assessed by transesophageal echocardiogram will also be acceptable if deemed necessary by the treating investigator.

10.7 Laboratory Assessments

Samples for all laboratory assessments will be drawn at the time points indicated in the Schedule of Events and when clinically indicated. Laboratory tests may be performed up to 3

days prior to the scheduled clinic visit. All safety laboratory analyses will be performed by the local laboratory for each study center or the subject's local laboratory per the schedule of events. All safety laboratory assessments must be reviewed by the treating investigator prior to study drug administration. When applicable, results from the pregnancy test must also be available for review prior to dosing.

Table 6: Laboratory Assessments

Laboratory Assessments	
CBC with Platelet Count and Differential (Hematology)	
 • White Blood Cell Count • Hemoglobin • Hematocrit • Red Blood Cell Count • Mean Corpuscular Volume • Red Cell Distribution Width • Platelets • Absolute Neutrophil Count and % • Absolute Lymphocyte Count and % • Absolute Monocyte Count and % • Absolute Basophil Count and % • Absolute Eosinophil Count and %
Chemistry	
 • Creatine Kinase • LDH • Magnesium • Phosphorus • Uric Acid • Complete Metabolic Panel (CMP) 
 ○ Sodium ○ Potassium ○ Chloride ○ Carbon Dioxide ○ Alkaline Phosphatase ○ Aspartate Aminotransferase ○ Alanine Aminotransferase ○ Urea Nitrogen ○ Glucose ○ Creatinine ○ Calcium ○ Protein ○ Albumin ○ Bilirubin ○ Anion Gap
Coagulation	
 • PT • INR

	
 • PTT
Hepatitis	
 • Hepatitis B Virus Core Antibodies • Hepatitis B Surface AG w/ reflex to confirm • Hepatitis C Virus Antibody • HIV 1,2 Antibodies
Pregnancy	Beta-hCG Qualitative Urine or Serum

10.8 Disease Assessment

Disease assessments will be conducted per the 2015 MDS/MPN-IWG criteria. Disease assessments will require bone marrow biopsy, aspirate, and the Myeloproliferative Neoplasm Symptom Assessment Form Total Symptom Score (MPN-SAF-TSS) as indicated in the Schedule of Events.

10.8.1 Bone Marrow Biopsy

Disease assessments will include bone marrow biopsy and aspirate at the time points indicated on the Schedule of Events. To facilitate timely review of results, bone marrow biopsies may be performed \pm 3 days from D21 of cycles as indicated in the Schedule of Events. At minimum, marrow and aspirate testing should include leukocyte and lymphocyte flow cytometry, chromosome analysis, mutational next-generation sequencing (NGS) panel, FLT3-ITD PCR and fluorescence in situ hybridization (FISH) for myeloproliferative disease (MPD). The following data points should be recorded in the corresponding eCRF.

- Blast, monoblast, and promonocyte count
- Any NGS and/or PCR identified mutations with corresponding allele frequency
- Percent cellularity
- Bone marrow fibrosis grade
- Cytogenetics
- FISH. For sites that do not have a MPD FISH panel, a BCR-ABL1 PCR may be completed.

10.8.2 Myeloproliferative Neoplasm Symptom Assessment Form Total Symptom Score (MPN-SAF-TSS)

The MPN-SAF-TSS will be administered at the time points indicated on the Schedule of Events. The MPN-SAF-TSS should be completed prior to meeting with the treating investigator.

10.9 Ophthalmologic Exam

A full ophthalmic examination with pupil dilation will be performed at the time points described in the Schedule of Events and will include best-corrected distance visual acuity

(BCVA), an automated threshold visual field (VF) of the central 10 degrees (with retesting if an abnormality is noted), and spectral-domain ocular coherence tomography (SD-OCT).

All ophthalmology assessments may be conducted ≤ 7 days prior to the clinic visit to enable results to be available for review.

11 CRITERIA FOR EVALUATION AND ENDPOINT

11.1 Safety

Routine safety and tolerability will be evaluated from the results of reported signs and symptoms, scheduled physical examinations, vital sign measurements, and clinical laboratory test results. More frequent safety evaluations may be performed if clinically indicated or at the discretion of the investigator.

11.2 Efficacy

Overall response criteria are based on the Myelodysplastic/Myeloproliferative (MDS/MPN) International Working Group 2015 consortium proposal for response criteria for myelodysplastic/myeloproliferative neoplasms in adults (Appendix 3).

11.3 Stopping Rules

The trial will be evaluated quarterly for excess toxicity. A rate of 20% grade 3 or higher non-hematological toxicity is acceptable, while a rate of 30% is unacceptable. The trial will be stopped if more than 2/5, 3/9, 4/13, 5/17, 6/22, 7/26, or 8/29 patients experience grade 3 or higher non-hematologic adverse events **attributed to study therapy** which are not improved or resolved with standard interventions such as dose hold, dose reduction or pharmacologic therapy (e.g. diuretic therapy) and continue to pose a significant clinical risk to the patient as determined by both the PI and medical monitor. The operating characteristics presented below were calculated using the R function “toxbdry” in the package “clinfun”. The output in the table below is from toxbdry(0.15, 0.4, c(5,9,13,17,22,26,29), cP0=0.1, cP1=0.9, ngrid=6).

Table 7: Operating characteristics of Stopping Rule (N = 29)

Operating characteristics of Stopping Rule			
Probability of DLT	Probability of Crossing Boundary	Probability of Stopping Before Last Patient	Expected Sample Size
0.15	0.089	0.087	27.5
0.20	0.238	0.230	25.4
0.25	0.449	0.431	22.3
0.30	0.664	0.641	18.8
0.35	0.829	0.808	15.4

0.40	0.929	0.914	12.6
------	-------	-------	------

11.4 Statistical hypothesis

We hypothesize that treatment with MEK inhibitor will produce a superior overall response rate in newly diagnosed and HMA-refractory CMML patients with RAS pathway activation compared to HMAs.

11.5 Sample size determination

Simon's two-stage design²⁸ will be used for both cohorts. In the newly diagnosed patients, the null hypothesis that the true response rate is 0.35 will be tested against a one-sided alternative. In the first stage, 9 patients will be accrued. If there are 3 or fewer responses in these 9 patients, the study will be stopped. Otherwise, 5 additional patients will be accrued for a total of 14. The null hypothesis will be rejected if 7 or more responses are observed in 14 patients. This design yields a type I error rate of 0.1678 and power of 0.8028 when the true response rate is 0.59.

In the HMA refractory patients, the null hypothesis that the true response rate is 0.10 will be tested against a one-sided alternative. In the first stage, 6 patients will be accrued. If there are 0 responses in these 6 patients, the study will be stopped. Otherwise, 9 additional patients will be accrued for a total of 15. The null hypothesis will be rejected if 3 or more responses are observed in 15 patients. This design yields a type I error rate of 0.1559 and power of 0.8100 when the true response rate is 0.30.

At the time of interim analysis per the two-stage design re-evaluation of the starting dose of cobimetinib will be considered should the rates of treatment-related Grade 3/4 non-hematologic AEs be higher than what was reported in the Diamond et al study²⁵.

11.5.1 Population for analyses

A modified intent-to-treat data set will be employed to analyze all toxicity and efficacy endpoints. All patients who have received one dose of cobimetinib will be considered evaluable for primary and secondary endpoints.

11.6 Statistical Analyses

11.6.1 Primary endpoint

The primary endpoint is overall response rate according to the 2015 MDS/MPN-IWG criteria. Overall response rate (ORR) will encompass patients achieving a complete remission, complete cytogenetic remission, partial remission, marrow response and clinical benefit as per these criteria.

Simon's two-stage design (Simon, 1989) will be used for both cohorts. In the newly diagnosed patients, the null hypothesis that the true response rate is 0.35 will be tested against a one-sided alternative. In the first stage, 9 patients will be accrued. If there are 3 or fewer responses in these 9 patients, the study will be stopped. Otherwise, 5 additional patients will be accrued for a total of 14. The null hypothesis will be rejected if 7 or more

responses are observed in 14 patients. This design yields a type I error rate of 0.1678 and power of 0.8028 when the true response rate is 0.59.

In the HMA refractory patients, the null hypothesis that the true response rate is 0.10 will be tested against a one-sided alternative. In the first stage, 6 patients will be accrued. If there are 0 responses in these 6 patients, the study will be stopped. Otherwise, 9 additional patients will be accrued for a total of 15. The null hypothesis will be rejected if 3 or more responses are observed in 15 patients. This design yields a type I error rate of 0.1559 and power of 0.8100 when the true response rate is 0.30. Two-sided 90% and 95% exact binomial confidence intervals will be reported separately for the newly diagnosed and HMA refractory patients.

11.6.2 Secondary endpoint

Secondary endpoints will be analyzed descriptively. Each secondary endpoint will be analyzed for all patients together as well as stratified into newly diagnosed and HMA refractory subgroups.

- The frequency of adverse events (AEs) characterized by seriousness, severity (as defined by CTCAE, version 5.0), duration, and relationship to study therapy. The frequency of AEs will be tabulated. The proportion of patients with AEs will be tabulated.
- The proportion of patients achieving CR + PR at any time point. The proportion of patients achieving CR will be reported along with 90% and 95% exact binomial confidence intervals.
- Progression-free survival (PFS) from the time of treatment initiation to 36 months after the start of therapy, the time of progression, initiation of alternative treatment, or death. Kaplan-Meier methods and associated confidence intervals will be used to analyze PFS. Subjects who move to follow-up after Amendment 6 (v.09DEC2025) and are able to obtain cobimetinib at the same dose and frequency per SOC will continue to be included in the analysis of PFS.
- Overall survival (OS) as defined as the time from the initiation of study therapy until death from any cause. Kaplan-Meier methods and associated confidence intervals will be used to analyze OS.

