4 STUDY DESIGN

4.1 Description

This is an open-label, nonrandomized phase 2 trial to assess the efficacy of cobimetinib in RAS pathway activated CMML. Two cohorts of patients will be accrued using Simon's two-stage design (Simon, 1989) for both cohorts. Cohort 1 will enroll nine newly diagnosed patients in the first stage and if four or more responses are observed five additional patients will be enrolled in the second stage. Cohort 2 will enroll six HMA refractory patients in the first stage and if one or more responses are observed then nine additional patients will be enrolled in the second stage. Study treatment safety will be periodically monitored for excessive toxicity as described in Section 11.3.

Table 2: Cohort Enrollment

Cohort	Stage 1 (n)	Stage 2 (n)
Cohort 1: Newly Diagnosed	9	5
Cohort 2: HMA Refractory	6	9

All eligible patients will be treated daily with cobimetinib in 28-day cycles. Cobimetinib will be administered consecutively for three weeks followed by a one week break prior to the start of the following cycle. Patients will remain on study therapy until treatment discontinuation criteria is met.

Due to discontinuation of cobimetinib supply from the benefactor, study participants who are currently on treatment will discontinue study cobimetinib early under Amendment 6 (v.09DEC2025). These subjects will discontinue treatment and proceed to EOT and Follow-Up.

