¹³ ECGs should be conducted at screening, C2D1, every three months while on study therapy (i.e. C5D1, C8D1, C11D1), and at the EOT visit. QTc will be calculated using the Fridericia calculation.

¹⁴ Ophthalmologic exams will be performed at screening, C2D1, every three cycles until cycle 11 (i.e., C5D1, C8D1, and C11D1), every four cycles from cycle 11 through cycle 23 (i.e., C15D1, C19D1, and C23D1), and then every six cycles until treatment discontinuation (i.e., C29D1, C35D1, C41D1, etc.). Ophthalmologic exams should be conducted ≤ 7 days prior to initiation of the next cycle of therapy.

¹⁵ Ophthalmologic exam does not need to be performed at the end of treatment visit if an evaluation has been performed within the last 12 weeks and there are no clinically significant findings and/or changes from baseline.

¹⁶ Adverse event collection should begin with the first dose of study drug and end 30 days after the last dose of study drug.

¹⁷ Patients will be contacted every three months (± 14 days) from the EOT visit until 36 months has elapsed from the initiation of study therapy. For subjects who went off study treatment per Amendment 6, cobimetinib dosing information should be collected.

¹⁸ Patients on study therapy will undergo a bone marrow biopsy at screening, C3D21, C6D21, and C12D21. Patients who discontinue treatment early or continue treatment beyond 12 cycles will have an additional biopsy at EOT. Bone marrow biopsies may be conducted ± 3 days of Day 21; however, days 19-21 are preferred. Screening and end of treatment bone marrow studies include pathology, flow cytometry, NGS, FLT3-ITD PCR, FISH and cytogenetics. On-treatment bone marrow studies include pathology, flow cytometry, NGS, FLT3-ITD PCR, and cytogenetics. FLT3-ITD PCR will not be required for on-treatment bone marrow studies if negative at screening. If clinically indicated, unscheduled samples may be collected following a discussion between the treating physician and the Principal Investigator.

¹⁹ Patients on study treatment will have MPN-SAF-TSS performed at screening, C3D21, C6D21, and C12D21. Patients who discontinue treatment early or continue treatment beyond 12 cycles as per Section 6.4 will have testing also performed at EOT. See Appendix 4.

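### PFS runs on past end of treatment for Amendment 6 patients, but no progression assessment is scheduled there, and the PFS definition does not separate events from censoring

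*Combined protocol and SAP*

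**What the plan says.** **Definition.** Sections 1.2.3 and 11.6.2 run PFS "from the time of treatment initiation to 36 months after the start of therapy, the time of progression, initiation of alternative treatment, or death". The method is Kaplan-Meier with confidence intervals. No censoring rule is given.

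**Amendment 6.** Section 4.1 and Table 5 footnote 2 take every patient still on treatment to EOT and then Follow-Up because supply ends. Section 11.6.2 adds that those who "are able to obtain cobimetinib at the same dose and frequency per SOC will continue to be included in the analysis of PFS". Section 9.4 agrees: "Community sourced cobimetinib will not be considered a new line of therapy if given at the same dose and frequency" as the protocol.

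**Data after EOT.** In Table 5 the Follow-up column is marked only for survival follow-up. Footnote 17 has patients "contacted every three months (± 14 days) from the EOT visit until 36 months has elapsed" since starting therapy, and adds: "For subjects who went off study treatment per Amendment 6, cobimetinib dosing information should be collected". Section 9.4 says that after progression or a new anticancer therapy, "patients will be followed for survival in long-term follow-up for a total of 36 months from the start of therapy".

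**What progression needs.** Section 10.8 bases disease assessment on the 2015 MDS/MPN-IWG criteria and requires marrow biopsy, aspirate and the MPN-SAF-TSS. Footnotes 18 and 19 schedule marrow and TSS on treatment (C3, C6, C12) and at EOT. Appendix 3 requires two major criteria, one major and two minor, or three minor, with blasts measured in marrow.

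**Population.** Section 11.5.1 makes every patient with one dose evaluable for primary and secondary endpoints.

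**The concern.** A Kaplan-Meier PFS curve treats a patient as progression-free for as long as he or she is at risk without a recorded event. Amendment 6 extends that time for one group but supplies no means of recording progression in it. Only death, or perhaps a new therapy, would then end their PFS, so their part of the curve drifts toward overall survival.

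Two gaps in the wording add to this. First, an analyst could score a responder's supply-forced switch as a failure or censor it, and comply with the text either way. Second, the Amendment 6 sentence covers only patients who obtain the drug at the same dose and frequency. It does not say what happens to those who obtain none or take it at another dose. If they drop out of the PFS analysis, this conflicts with Section 11.5.1 and makes inclusion depend on drug access after study treatment.

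PFS is one of two endpoints for the long-term efficacy objective. Progression dates not collected during follow-up may not be recoverable later.

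**Working it through.** **1. The plan's own figures.** The documents give no PFS median, event count or power. The only stated design figures are the Simon error rates for response. They reproduce (cohort 1: 0.1678 and 0.8028; cohort 2: 0.1559 and 0.8100) and do not depend on this point.

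**2. What is collected, and when.**

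| Needed for PFS | On treatment | EOT | Follow-up |
|---|---|---|---|
| Marrow, cytogenetics | C3, C6, C12 | yes, if early or beyond 12 cycles | not scheduled |
| MPN-SAF-TSS | C3, C6, C12 | yes, if early or beyond 12 cycles | not scheduled |
| Blood counts, physical exam | each cycle | yes | not scheduled |
| Survival | – | – | every 3 months |
| Cobimetinib dosing | diary | – | Amendment 6 patients |

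The same empty cells apply to a patient stopped for toxicity or after 12 cycles without progression. The gap therefore predates Amendment 6, which widens it.

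**3. Illustration of size.** From the documents: 29 patients (Section 4.2); 29 months, the upper end of the median OS range in Section 2.1; the 36-month limit. Assumed:
- exponential times, with true median PFS *m* of 8, 12 or 18 months;
- time *c* from a patient's start to Amendment 6 uniform on 0 to *a* months, *a* = 36 or 54;
- every patient event-free at *c* < 36 is still on treatment (this overstates the number affected if some had already stopped);
- switches occur one month after stopping.

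Hazards per month: λD = ln2/29 = 0.02390 (death), λT = ln2/*m* (PFS), λG = λT − λD (progression). Nothing is censored before month 36, so the expected 24-month estimate is the share with recorded time above 24.

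- True: S = exp(−24λT).
- (A) Affected patients stay at risk, only deaths seen: [exp(−24λD)·(1 − exp(−24λG))/λG + (a − 24)·S]/a.
- (B) All affected patients switch, each switch an event: [(exp(−23λT) − exp(−24λT))/λT + (a − 24)·S]/a.

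For *m* = 8, *a* = 36:
- S = 0.125.
- A = [0.5635 × (1 − 0.2218)/0.06274 + 12 × 0.125]/36 = (6.989 + 1.500)/36 = 0.236.
- B = (0.131 + 1.500)/36 = 0.045.

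| m | a | True | A | Error (points) | B | Error (points) | Half switch, half as A: error (points) |
|---|---|---|---|---|---|---|---|
| 8 | 36 | 0.125 | 0.236 | +11.1 | 0.045 | −8.0 | +1.6 |
| 8 | 54 | 0.125 | 0.199 | +7.4 | 0.072 | −5.3 | +1.0 |
| 12 | 36 | 0.250 | 0.341 | +9.0 | 0.091 | −16.0 | −3.5 |
| 12 | 54 | 0.250 | 0.310 | +6.0 | 0.144 | −10.6 | −2.3 |
| 18 | 36 | 0.397 | 0.449 | +5.2 | 0.144 | −25.3 | −10.1 |
| 18 | 54 | 0.397 | 0.432 | +3.5 | 0.228 | −16.9 | −6.7 |

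A simulation of 29 patients (4,000 runs per setting) agrees with these values. It had 5.9 to 15.7 patients affected on average. Median PFS was 0.5 to 2.4 months too long under A and 1.3 to 7.7 months too short under B.

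**4. Check of the remedy.** In the same simulation, censoring all affected patients at their last assessment gave 24-month PFS within 0.5 point of the truth and the median within about 0.2 month. This assumes that stopping for lack of supply is unrelated to prognosis.

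**The case against.** Several stronger readings are tempting, and the documents do not support them.

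- **Follow-up records survival and nothing else.** Footnote 17 and Section 9.4 also call for cobimetinib dosing. Section 9.4 starts survival follow-up at progression or new therapy, which presumes that these are known, and names medical records as a source, though only for survival status. Appendix 3 also allows progression on three minor criteria, some of which need no marrow (transfusion dependence, a fall in hemoglobin). What stands is narrower: no progression assessment is scheduled, and no field for it is specified, after EOT.
- **A supply-forced switch counts as progression.** The text never says so. The same list holds the 36-month limit, which can only be censoring, so being listed does not make something an event. Community cobimetinib at the protocol dose and frequency is expressly exempt. If switches are censored, error B largely disappears. What stands is that the text permits either scoring.
- **PFS will be biased by a known amount, or cannot be interpreted.** The numbers on treatment at Amendment 6 and later switching are not given, and either may be small. The two errors oppose each other. One could set the documents' OS range against an assumed short PFS after EOT and obtain a much larger gap. That contrast would cover only affected patients after EOT, whereas protocol PFS starts at treatment initiation and includes everyone.
- **Amendment 6 caused the problem.** The follow-up gap already existed for patients stopped without progression.

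It is also fair to say that PFS is descriptive, with no test, in cohorts of 14 and 15.

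**Conclusion.** The point holds in limited form. Followed as written, the plan keeps some patients at risk for PFS while their progression goes largely unrecorded, which raises their PFS. It also leaves open whether alternative treatment is an event, and how patients who cannot obtain the drug are handled, although Section 11.5.1 makes them evaluable.

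Under the assumptions above, the error in 24-month PFS is about +3.5 to +11 points if only deaths are seen, and about −5 to −25 points if all affected patients switch and switches are events. With half switching it runs from about +1.6 to −10. The documents fix neither the net direction nor the size. These figures illustrate what is at stake and do not predict this trial's result.

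This should be fixed but is not critical: it concerns one descriptive secondary endpoint. ORR, OS and the Simon error rates do not depend on it.

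**What to change.** In Sections 1.2.3 and 11.6.2:

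1. State that PFS events are progression by Appendix 3 and death, and that month 36 is administrative censoring.
2. Censor every dosed patient with no later documented disease assessment at the last adequate one (normally EOT), whether or not cobimetinib is obtained. Say that this also applies when death follows without an intervening assessment: counting those deaths while censoring survivors at EOT would bias the curve. Such deaths still count in OS.
3. Give one rule for alternative therapy started without progression, covering every reason for stopping (supply, toxicity, 12 cycles, other). Supply-forced switches are censored at the last assessment.
4. Add progression status and date, taken from medical records, to the existing three-monthly contacts. Patients on community cobimetinib then stay at risk for as long as their records document disease status.
5. Report the composite with alternative treatment as an event as a sensitivity analysis. It also guards against informative censoring when the stop was for reasons other than supply.

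The cost is a few sentences, one eCRF field and no added procedure. The price is more censoring and wider intervals. The wording should be settled before PFS results are seen, and the field added while follow-up is still running.
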